## Major Protocol Deviation List

| Deviation Category        | Deviation Description   | Date Deviation Added | Exclude from Per Protocol Population  |
|---------------------------|---|----------------------|---|
| Informed consent criteria | Subject did not sign informed consent before the initiation of study procedures (including deviations regarding protected health information / data protection forms (e.g. PHI, PIPEDA etc.)  | 16 Mar 2021          | No  |
| Eligibility criteria      | 
Subject was randomized without meeting one or more entry criteria
 
 
1. Genetically confirmed PH
 
2. Uox >0.7
 
3. Less than 20% variation in Ucr
 
4. eGFR >30
 
5. Agree to use contraception and not pregnant
 
6. Prior renal/liver transplant
 
7. Dialysis
 
8. Pox>30
 
9. Systemic oxalosis
 
10. Intercurrent illness
 
11. Active liver disease
 
12. Alcohol/Drug of abuse intake
 
13. Serious mental illness
 
14. Relevant history of disorders including dermatitis and connective tissue disorder
 
 | 16 Mar 2021          | 
 
1. Genetically confirmed PH -Yes, those not confirmed with PH should be excluded
 
2. Uox <0.7 should be excluded - Yes
 
3. More than 20% variation in Ucr should be excluded- Yes
 
4. eGFR <30 should be excluded- Yes
 
5. Agree to use contraception and not pregnant – No
 
6. Prior renal/liver transplant should be excluded- Yes
 
7. Dialysis should be excluded - Yes
 
8. Participants with Pox>30 should be excluded- Yes
 
9. If they have Systemic oxalosis should be excluded - Yes
 
10. Intercurrent illness - No
 
11. Active liver disease - No
 
12. Alcohol/Drug of abuse intake – No
 
13. Serious mental illness- No need to exclude if not affecting urine collection
 
14. Relevant history of disorders including dermatitis and connective tissue disorder - No
 
 |

| Deviation Category           | Deviation Description  | Date Deviation Added | Exclude from Per Protocol Population  |
|-------------------------------------|---|-----------------------------|--|
| Eligibility criteria
(continued) | 15. Use of RNAi in past 6 months
16. Prior history of reaction to RNAi
17. Pyridoxine dose not stable for 4 weeks prior to enrolment
18. Clinical study participation in the past 4 months (if related to Uox need to return to baseline)
19. LFT abnormalities
20. Positive viral screen
21. Positive drug screen
22. Hypersensitivity to DCR-PHXC
23. Unwilling to comply with section 5.3 – vitamin C intake, follow standard of care, refrain from exercise, avoid oxalate rich foods | 16 Mar 2021                 | 15. Use of RNAi in past 6 months – No not unless it is Lumasiran
16. Prior history of reaction to RNAi – No, as long as no reaction is noted during the study
17. Those whose Pyridoxine dose was not stable for 4 weeks prior to enrolment should be excluded - Yes
18. Clinical study participation in the past 4 months (if related to Uox need to return to baseline) – Yes if participant did not have Uox back at baseline it should be excluded
19. LFT abnormalities - No
20. Positive viral screen - No
21. Positive drug screen - No
22. Hypersensitivity to DCR-PHXC- Yes participant should be excluded as study drug may not be effective
23. Unwilling to comply with section 5.3 – vitamin C intake, follow standard of care, refrain from exercise, avoid oxalate rich foods – Yes participants who are not compliant should be excluded |
| IP criteria                         | Patient received and dosed incorrect drug   | 16 Mar 2021                 | Yes (if subject received less than 5 or more than 7 doses)   |
| IP criteria                         | Subject received IP despite failure to adhere to the storage, preparation, or handling of study drug according to the protocol and assessed as non-acceptable by quality assurance  | 16 Mar 2021                 | Yes (if more than 1 dose is affected and assessed as non-acceptable by QA).  |

| Deviation Category       | Deviation Description   | Date Deviation Added | Exclude from Per Protocol Population  |
|---------------------------------|--|-----------------------------|--|
| IP Criteria                     | Subject received IP despite discontinuation or withdrawal criteria   | 16 Mar 2021                 | No   |
| Concomitant medication criteria | The subject used prohibited concomitant medications or therapies   | 16 Mar 2021                 | Yes, for medications that can affect efficacy (e.g. Lumasiran, vitamin C)

No, for medications that can affect safety (e.g. acetaminophen) |
| Efficacy evaluation criteria    | Subject is missing 2 or greater Uox assessments during the period from day 90 to day 180

Subject is missing 3 Uox assessments in a row at any given point                                     | 16 Mar 2021                 | Yes  |
| Efficacy evaluation criteria    | Subject has greater than 20% variance in 2 or greater Uox assessments during the period from day 90 to day 180

Subject has greater than 20% creatinine variance in 3 Uox assessments in a row | 16 Mar 2021                 | Yes  |
| Efficacy evaluation criteria    | Subject did not collect 24 hour urine for full 24 hours and did not perform a repeat for 2 timepoints between day 90 to day 180 or 3 times in a row  | 16 Mar 2021                 | Yes  |
| Safety monitoring               | Subject is a child-bearing female who missed a pregnancy test prior to dosing and was pregnant on the subsequent pregnancy test.   | 16 Mar 2021                 | No   |

| Deviation Category | Deviation Description   | Date Deviation Added | Exclude from Per Protocol Population |
|---------------------------|--|-----------------------------|---|
| Safety reporting          | Subject's SAE was reported late or was not reported  | 16 Sep 2020                 | No  |
| Other criteria            | The subject or site was accidentally unblinded to the subject's treatment information during the study.    | 16 Sep 2020                 | Yes   |
| Other criteria            | Any deviations that constitute fraud, scientific misconduct or Serious Breach will be classified as major. | 16 Sep 2020                 | Yes   |

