9.4. POPULATIONS FOR ANALYSES

For purposes of analysis, the following populations are defined:

- **Enrolled:** The enrolled population includes all participants who sign the ICF.
- **Safety Population:** The safety population includes all participants randomly assigned to study intervention and who take at least 1 partial or full dose of study intervention. Participants will be analyzed according to the intervention they actually received.
- **Intent-To-Treat Population (ITT):** The ITT population includes all participants who were randomized and have at least one post-baseline efficacy assessment. Participants will be analyzed according to the intervention they were randomized to.
- **Modified Intent-To-Treat Population (MITT):** The MITT population includes all participants in the ITT population who have at least one efficacy assessment after the Day 90 dosing visit.
- **Evaluable:** The evaluable population includes all participants who received 6 full doses of study intervention and completed the study.
- **Pharmacokinetic Population:** The PK Population includes all participants in the Safety Population without major dosing violations. Details will be provided in the Pharmacokinetics Analysis Plan (PKAP).

- **Per Protocol (PP):** The PP Population includes all participants who received 6 full doses of study intervention, had no major protocol deviations, and completed the study.

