| Urine drug screen h                | X                         |           |   |            |            |                 |            |            |            |             |             |             |    |
| Viral serology i                   | X                         |           |   |            |            |                 |            |            |            |             |             |             |    |
| FSH (postmenopausal women)                    | X                         |           |   |            |            |                 |            |            |            |             |             |             |    |
| Study intervention administration             |                           | X         |   |            | X          |                 |            | X          | X          | X           | X           |             |    |
| Spot urine collection j            | X                         |           |   |            | X          |                 |            | X          | X          | X           | X           | X           | X  |
| 24-hr urinary oxalate k            | X                         |           |   |            | X          |                 |            | X          | X          | X           | X           | X           | X  |
| 24-hr urinary creatinine l         | X                         |           |   |            | X          |                 |            | X          | X          | X           | X           | X           | X  |
| Blood draw for vitamin B6 levels m |                           | X         |   |            | X          |                 |            | X          | X          | X           | X           | X           |    |
| Plasma PK sample n                 |                           | X         | X |            | X          | X               |            |            |            |             | X           |             | X  |
| Plasma oxalate sample o            | X                         | X         |   |            | X          |                 |            | X          | X          | X           | X           | X           | X  |
| Record fluid intake p              | X                         | X         |   |            | X          |                 |            | X          | X          | X           | X           | X           |    |

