## 5. Analysis Populations

The following analysis populations are planned for this study:

- **Randomized Population (RAND):** The randomized population includes all participants who were randomized.
- **Enrolled Population (ENRL):** The enrolled population includes all participants who sign the informed consent form.
- **Safety Population (SAF):** The safety population includes all participants randomly assigned to study intervention and who take at least one partial or full dose of study intervention. Participants will be analyzed according to the intervention they actually received.
- **Intent-To-Treat Population (ITT):** The ITT population includes all participants who were randomized and have at least one postbaseline efficacy assessment. Participants will be analyzed according to the intervention they were randomized to.
- **Modified Intent-To-Treat Population (MITT):** The MITT population includes all participants in the ITT population who have at least one efficacy assessment after the Day 90 dosing visit.
- **Evaluable Population (EVAL):** The evaluable population includes all participants who received 6 full doses of study intervention and completed the study.

- **Pharmacokinetic Population (PK):** The PK population includes all participants in the safety population without major dosing violations. Details will be provided in the PKAP.
- **Per-Protocol Population (PP):** The PP population includes all participants who were randomized and had no major protocol deviations that affect efficacy endpoint assessment as adjudicated by the sponsor.

The primary and the key secondary efficacy analyses will be performed on the MITT population and repeated in further analysis populations as described in section 8.

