### 7.2. Protocol Violations and Deviations

Prior to database lock and unblinding, all protocol deviations will be reviewed and categorized as either 'Important' or 'Non-important':

- Important PDs are a subset of protocol deviations that may significantly impact the completeness, accuracy, and/or reliability of key study data or that may significantly affect a subject's rights, safety, or well-being.
- Non-important PDs will be identified as any protocol deviation that does not meet the criteria for Important PD.

Subjects with at least 1 deviation classified in the major protocol deviation list included in the appendix to this SAP will be excluded from the PP analysis population.

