### 8.1. Primary Efficacy Analysis

The primary efficacy endpoint of this study is the  $AUC_{24\text{-hour } U_{ox}}$  from Day 90 to Day 180, based on percent change from baseline. The primary endpoint will be compared between the active treatment group and the placebo group.

This is a superiority study. For the primary endpoint, the null hypothesis to be tested is:

- $H_0: AUC_{24\text{-hour } U_{ox, a}} = AUC_{24\text{-hour } U_{ox, p}}$  against one-sided alternative hypothesis
- $H_A: AUC_{24\text{-hour } U_{ox, a}} > AUC_{24\text{-hour } U_{ox, p}}$ .

where

- $AUC_{24\text{-hour } U_{ox, a}}$  is the  $AUC_{24\text{-hour } U_{ox}}$  for the active treatment arm (DCR-PHXC),
- $AUC_{24\text{-hour } U_{ox, p}}$  is the  $AUC_{24\text{-hour } U_{ox}}$  for the placebo arm

All hypotheses will be tested at the one-sided significance level alpha of 2.5%.

Mean  $AUC_{24\text{-hour } U_{ox}}$  from Day 90 to Day 180 will be compared between treatment groups using an ANCOVA model with treatment group as a main effect in the model; and age category [6 to 11, 12 to 17, or  $\geq 18$  years], eGFR category [ $< 45$  mL/min or  $\geq 45$  mL/min], and baseline  $U_{ox}$  as covariates, where the BSA adjustment is applied to the 24 hour urinary oxalate values for all pediatric subjects. The adjusted means for each treatment will be presented together with their 95% confidence intervals. The adjusted mean difference will be presented along with its 95% confidence interval and p-value.

The primary efficacy analysis will be based on the MITT dataset. This analysis will be repeated for the PP population and in addition as sensitivity analyses in ITT and EVAL population (see section 8.5).

$U_{ox}$  concentrations which do not meet completeness criteria (see section 6.1.5.2) will be excluded from the primary efficacy analysis. Multiple imputation will be used for those excluded values as well as for all other missing values.

Descriptive statistics for actual  $U_{ox}$  concentrations and for percent change from baseline will be presented by visit.

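### The per-protocol rule for wrong-drug dosing counts doses received, not wrong-drug doses, and conflicts with SAP section 7.2; separately, the SAP drops the protocol's dose and completion requirements for that set

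*SAP*

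**What the plan says.** The SAP's Major Protocol Deviation List has an IP-criteria row for the deviation "Patient received and dosed incorrect drug". Its entry in the PP-exclusion column is "Yes (if subject received less than 5 or more than 7 doses". The next row, on storage, preparation and handling, is framed differently: "Yes (if more than 1 dose is affected and assessed as non-acceptable by QA".

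Three other places define who is in the PP set:

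- SAP section 7.2: "Subjects with at least 1 deviation classified in the major protocol deviation list included in the appendix to this SAP will be excluded" from PP. No threshold is given, and the list's Yes/No column is not mentioned.
- SAP section 5: PP is everyone randomized who "had no major protocol deviations that affect efficacy endpoint assessment as adjudicated by the sponsor". There is no dose or completion requirement.
- Protocol section 9.4: "The PP Population includes all participants who received 6 full doses of study intervention, had no major protocol deviations, and completed the study".

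SAP section 10, on changes from the planned analysis, reports none. SAP section 8.1 puts the primary analysis on MITT and adds: "This analysis will be repeated for the PP population".

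**The concern.** A per-protocol set is meant to show the effect in participants treated as assigned. For the deviation that bears most directly on that, the row asks how many doses were received and not how many were of the wrong drug. Read as written, it can keep in PP a participant who never received the assigned treatment.

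The surrounding text does not resolve this, because section 7.2, section 5 and the list's exclusion column give three different rules. The SAP requires the populations to be defined before the blind is broken (section 4.3), so whoever applies these rules would have to choose among them.

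The SAP's section 5 definition also departs from the protocol without saying so. A participant with fewer than six full doses, or one who did not complete the study, could enter the SAP's PP set although the protocol's definition excludes them.

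**Working it through.** **Number of scheduled doses.** The protocol's PP definition gives 6. The row "Study intervention administration" in SAP Table 1 has marks at Days 1, 30, 60, 90, 120 and 150, which is 6. The two agree.

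**Applying the row.** Let d be the number of doses the row counts. The participant is out if d < 5 or d > 7, so d = 5, 6 or 7 is retained. The row does not say which doses d counts. For a participant dosed at all six visits, w of them with wrong drug, there are three possible readings:

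| Wrong doses w | d = all doses (6) | d = doses of assigned drug (6 − w) | d = wrong-drug doses (w) |
|---|---|---|---|
| 1 | in | in | out |
| 2 | in | out | out |
| 3 | in | out | out |
| 4 | in | out | out |
| 5 | in | out | in |
| 6 | in | out | in |

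- All doses (the plain wording): the number of wrong doses never matters, and w = 6 is retained.
- Doses of assigned drug: a sensible result. One error is tolerated and two or more exclude, but the row does not say this.
- Wrong-drug doses: perverse, since one to four errors exclude but five or six do not.

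The upper limb, more than seven, cannot arise from a six-dose schedule.

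**Comparing with section 7.2.** Under section 7.2 every value of w from 1 to 6 is out. Read literally, section 7.2 also excludes for rows whose exclusion column says No, such as consent deviations and late SAE reporting. Either section 7.2 makes the column meaningless, or the column governs and the row above applies.

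**Comparing the PP definitions.**

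| Requirement | Protocol 9.4 | SAP section 5 |
|---|---|---|
| Six full doses | yes | absent |
| Completed study | yes | absent |
| No major deviation | any | only those the sponsor judges to affect efficacy assessment |

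**Size of effect on the PP contrast.** Inputs from SAP section 3.2: planned AUC means 3600 (active) and 0 (placebo), 24 and 12 participants, effect size 1.2. The SAP states as-received assignment for the safety set and as-randomized for ITT, but neither for PP. As-randomized is assumed here, with no covariate adjustment and with the cross-treated participant having the mean response of the drug actually received.

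- One placebo participant on active throughout: the placebo mean becomes 3600/12 = 300 and the contrast 3600 − 300 = 3300, a loss of 300/3600 = 8.3%.
- One active participant on placebo throughout: the active mean becomes 3600 × 23/24 = 3450, a loss of 150/3600 = 4.2%.
- Implied SD 3600/1.2 = 3000; standard error of the difference 3000 × √(1/24 + 1/12) ≈ 1061. The shifts are 300/1061 ≈ 0.28 and 150/1061 ≈ 0.14 standard errors.

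**The case against.** A reader might infer that a participant wrongly dosed at every visit is certain to remain in PP, and leaves only if the total is below five or above seven. The documents do not support that. Section 7.2 would exclude after a single listed deviation. Section 5 lets the sponsor judge that six wrong doses affect efficacy assessment. If the row means doses of assigned drug, such a participant has none and is out; one tolerated error would then match the adjacent row's threshold of more than one. All of this stands, and it limits the finding to the row's plain wording and its conflict with the other text. It does not rescue the row, which does not state that reading and whose upper limb remains odd.

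A reader might also blame this row for the departure from the protocol's six-dose rule. The row covers only wrong-drug events. The departure comes from the SAP section 5 definition, so editing the row alone would leave it in place.

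Three points on impact also stand:

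- Six consecutive errors are unlikely, given central IWRS assignment and a second-person check of each preparation (protocol sections 6.3 and 6.2.4).
- The evaluable set keeps the six-dose and completion requirements, and SAP section 8.5 repeats the primary analysis on it. That partly covers the dose-count gap, though not wrong-drug dosing.
- Cross-treatment dilutes toward no difference, which is conservative in a superiority trial. Tolerating one wrong dose in a supportive set is a legitimate choice if it is stated.

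**Conclusion.** The concern holds as a defect in the written rule. On its plain wording the wrong-drug row decides PP membership by a dose count unrelated to how many doses were wrong, and so retains a participant wrongly dosed at all six visits. It contradicts section 7.2 and sits beside a definition that rests on adjudication. Separately, SAP section 5 omits two requirements of the protocol's PP definition, and section 10 does not record the change.

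The consequence is small. The primary and key secondary analyses use MITT, and PP has no place in the hierarchical testing sequence. The 8.3% and 4.2% shifts are illustrations for one participant cross-treated throughout, at the planned means and allocation and under the as-randomized assumption. The documents give no likelihood for such an event. The point is minor, but the text should be reconciled before the populations are fixed.

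**What to change.** 1. In the Major Protocol Deviation List, make PP exclusion for incorrect drug depend on the number of wrong-drug doses, with the threshold fixed before unblinding: for example any such dose, or more than one as in the adjacent row. Put missed or excess doses of assigned drug in a separate row.
2. Reword SAP section 7.2 so that only deviations marked Yes in the exclusion column, with any stated condition met, remove a participant from PP.
3. Restore the protocol's six-dose and completion requirements in SAP section 5, or record and justify the change in section 10.
4. State whether PP participants are analysed as randomized or as treated.

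The cost is a few lines of SAP text. The PP set may be one or two participants smaller.

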### 6.1.5. Handling of Dropouts or Missing Data

#### 6.1.5.1. Missing Efficacy Endpoint Data

While all possible efforts will be made to ensure that participants stay in the study and all data is collected as scheduled, the occurrence of missing data cannot be completely eliminated.

For the analysis of AUC related efficacy endpoints, based on the MITT or ITT populations, a multiple imputation (MI) approach under the missing-at-random (MAR) assumption will be used to handle missing endpoint data. Subsequently, the AUC related efficacy endpoints will be calculated.

That is, any participant who withdraws or is discontinued from the study or who misses a scheduled visit or assessment through Day 180 will have their missing AUC related efficacy data analyzed as imputed using MI techniques.

Multiple imputation based on a standard MAR imputation approach will be performed in SAS® software using the general approach described below. This strategy is appropriate for data sets that have an arbitrary missing data pattern.

*Step 1:* The Missing at Random (MAR) imputation model will impute missing values using a fully conditional specification (FCS) regression-based multiple imputation model. For participants with missing data at a particular visit, a multiple regression model will be fit that includes the outcome at that visit as the dependent variable and observed data (e.g., outcomes at other visits, treatment, age category [6 to 11, 12 to 17, or ≥18 years], eGFR category [<45 mL/min or ≥45 mL/min], and baseline value of the primary response variable (e.g., Uox or Uox-to-creatinine ratio) as independent variables. This process will be repeated 50 times, resulting in 50 complete analysis data sets. The seed number of 3216549 will be used for the imputation procedure described in Step 1.

SAS pseudo code is provided below:

```
PROC MI DATA=indata OUT=outdata SEED=3216549 NIMPUTE=50;  
  CLASS <treatment> <age category> <eGFR category>;  
  FCS REG (<day 90> <day120> <day 150> <day 180>);  
  VAR <treatment> <age category> <eGFR category> <baseline> <day 90> <day120>  
    <day 150> <day 180>;  
RUN;
```

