##### **Treatment Period 24-hour Urine Collection Completeness:**

As detailed in the Study Unblinded Clinical Monitoring Plan, certain members of the unblinded study team will conduct an ongoing review of treatment-period 24-hour urinary creatinine excretion values, to ensure all weight-adjusted 24-hour urinary creatinine excretion values are no more than 20% of baseline. If the percentage change in any weight-adjusted 24-hour urinary creatinine excretion values are more than 20% of baseline, then this is a violation of the completeness criteria. If weight is missing at a visit, LOCF (last observation carry forward) weight should be used in creatinine excretion values per kg calculation. Baseline is defined as the mean of the 2 screening values. Additionally, the site will review the 24-Hour Urine Collection Schedule worksheets completed by the participant. Any collection with a duration of less than 22 hours or greater than 26 hours will be considered invalid.

Should a treatment-period value not meet these criteria, participants will be required to complete another 24-hour urine collection. Recollection should occur within 10 calendar days from the time of the visit for which the collection was intended whenever possible. In the event the repeated 24-hour urine collection violates the completeness criteria, the 24-hour urine collection for that visit will not be repeated a second time.

For the analyses of AUC related endpoints, only 24 hour urine oxalate measurements that meet the completeness criteria will be used for each visit to calculate AUC. That usually would be the latest measurement in case of recollection if criteria are not met. In case there is more than one measurement that does not violate the completion criteria, the average will be taken.

Measurements that violate the completeness criteria will not be included in the AUC calculations. Rather those values will be treated as missing data and will be imputed via the MI methods described in section 6.1.5.1 prior to calculating the AUC values for analysis.

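### The per-protocol urine rows are counted separately and do not follow the SAP's completeness rule, so PP membership does not track how many valid Day 90–180 Uox values a participant has

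*SAP*

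**What the plan says.** SAP 8.1 runs the primary analysis on MITT and repeats it in PP. SAP section 5 defines PP as randomized participants without major deviations affecting efficacy assessment, as adjudicated by the sponsor. SAP 7.2 makes the appended list the exclusion rule.

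The primary window has four collections: "FCS REG (<day 90> <day120> <day 150> <day 180>". Under SAP 6.1.5.2 a treatment-period urine is usable only if weight-adjusted creatinine is within 20% of baseline and the collection lasted 22 to 26 hours. One repeat is allowed and no second. Of values that fail, the SAP says: "Rather those values will be treated as missing data and will be imputed via the MI methods described in section 6.1.5.1".

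The list has three efficacy-evaluation rows, each leading to exclusion from PP:

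- **Missed:** "Subject is missing 2 or greater Uox assessments during the period from day 90 to day 180", or "Subject is missing 3 Uox assessments in a row at any given point".
- **Creatinine:** "Subject has greater than 20% variance in 2 or greater Uox assessments during the period from day 90 to day 180", or "Subject has greater than 20% creatinine variance in 3 Uox assessments in a row". The first sentence does not name creatinine; I read it as the creatinine criterion because the second does.
- **Duration:** no collection for "full 24 hours and did not perform a repeat for 2 timepoints between day 90 to day 180", or the same three times in a row.

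**The concern.** For the AUC, the cause of an unusable value does not matter. For PP membership it does: each cause has its own threshold, nothing sums them, and the rows define failure differently from SAP 6.1.5.2. A participant with fewer valid values can therefore stay while one with more is removed. At stake is whether the PP repeat of the primary analysis rests on participants with better-observed endpoints, in a trial planned for 36, of whom 12 are on placebo.

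**Working it through.** The plan states no figure for this point, so the check compares the two rules, then enumerates patterns.

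**1. The rules side by side.**

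| Outcome at one visit | Usable under SAP 6.1.5.2? | Row that counts it |
|---|---|---|
| No collection | No | Missed |
| Creatinine failure, no valid repeat | No | Creatinine |
| Under 22 h, no repeat | No | Duration |
| Under 22 h, repeat also under 22 h | No | None |
| Over 26 h, creatinine within 20% | No | None |
| 23 h, creatinine within 20%, no repeat | Yes | Duration, read literally |
| Creatinine failure, then valid repeat | Yes | Creatinine, read literally |

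On the over-26 h line: a 27-hour collection gives 27/24 = 1.125, or +12.5% creatinine, if excretion is proportional to time, baseline collections ran 24 hours and weight is unchanged. That passes the 20% limit, and the urine did cover 24 hours, so no row applies whether or not it was repeated.

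**2. Separate counting alone.** Take four visits and four states: valid, missed, creatinine-failed, short without repeat. Days 30 and 60 are assumed valid. A run of three inside the window already meets the threshold of two, so the run criteria add nothing here.

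- Zero valid: 3^4 = 81 patterns. Four failures over three causes must repeat a cause, so all 81 are excluded.
- One valid: 4 × 3^3 = 108 patterns. Those with three different causes, 4 × 3! = 24, stay.
- Two valid: 6 × 3^2 = 54 patterns. Those with the same cause twice, 6 × 3 = 18, are removed.

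The ordering is therefore inverted: 24 one-valid patterns stay while 18 two-valid patterns go.

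**3. Adding the failed duration repeat.** Add a fifth state, short with a short repeat, which no row counts. There are 4^4 = 256 zero-valid patterns. Those retained use each of the other three causes at most once: 1 + 3×4 + 3×12 + 24 = 73. Every one contains at least one failed repeat. These are counts of patterns, not probabilities.

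**4. Size of the separate-counting effect.** Assume independent causes, each with probability p per visit of leaving no valid value, and v = 1 − 3p.

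- Two or more unusable: 1 − v^4 − 4(3p)v^3
- Retained with 2 of 4 valid: 36p²v²
- Retained with 1 of 4 valid: 24p³v

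| p | Two or more unusable | Retained, 2 valid | Retained, 1 valid | Retained, total | Of 36 |
|---|---|---|---|---|---|
| 2% | 1.99% | 1.27% | 0.02% | 1.29% | 0.5 |
| 5% | 10.95% | 6.50% | 0.26% | 6.76% | 2.4 |

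All percentages are of all participants. At 5%, 6.50/6.76 = 96% of those retained still have two valid values. With creatinine failures at 10% and the others at 5%, 18.1% have two or more unusable values and 10.1% are retained. If only one cause ever occurs, the effect is nil.

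**5. After the change.** With one combined count over the five states, all 256 zero-valid, all 256 one-valid and all 96 two-valid patterns are excluded; all 17 with three or four valid values stay. Removing only the repeat excuse is not enough: zero-valid patterns then all go, but 48 of 256 one-valid patterns stay while 36 of 96 two-valid patterns are removed.

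**The case against.** **Missing may include failed urines.** SAP 6.1.5.2 says failed values are treated as missing. If the missed row inherits that meaning, it alone removes every pattern with two or more unusable values. The other rows would then be largely redundant in this window, which favors the literal reading, but not wholly so: the creatinine row could still catch failures rescued by a repeat, and the duration row a 23-hour collection. The SAP leaves the reading open, and that ambiguity is itself a reason to reword.

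**Sponsor adjudication could catch such cases.** It could, and SAP 4.3 places it before unblinding. But no minimum number of valid values is stated for it to apply.

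**PP may be meant as an adherence set.** A participant who repeats once as instructed has followed the protocol, and no passage defines PP by data sufficiency. This is a fair defense of treating a failed repeat differently from a skipped visit. It does not explain why three different failures count for less than two of one kind, or why over-long collections fall outside every row.

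**The analysis is supportive.** PP is outside the hierarchy in SAP 6.1.4, and SAP 8.5 adds several other sensitivity analyses. SAP 6.1.5.1 names MITT and ITT for multiple imputation but not PP, so it is not settled that a zero-valid PP participant would be imputed. All of this stands and limits the weight of the point.

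**Stronger readings to avoid.** A reader might infer that any repeated collection is excused. Only the duration row has a repeat clause; two creatinine failures exclude whether or not they were repeated. A reader might also infer that separate counting alone can keep someone with no valid data, or that the percentages above describe such people. Step 2 rules out the first, and the model in step 4 contains no route to the second.

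**Conclusion.** The point holds as a mismatch between the PP rows and the completeness rule. On the literal wording, separate counting lets a participant with 1 of 4 valid values stay while one with 2 of 4 is removed; this needs no assumption about rates. Zero-valid retention is possible only through failed duration repeats or over-long collections, and no probability can be attached to it. In the other direction, the rows can count a valid 23-hour urine, or a creatinine failure later rescued by a valid repeat, against a participant.

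The size, 1.3–6.8% of all participants retained with two or more unusable values, rests on assumed independent rates of 2–5% per cause that the documents do not supply. The primary MITT result is untouched. This is worth correcting, with modest consequences.

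**What to change.** Replace the three rows with one definition: a visit counts if, whatever the cause, it has no 24-hour Uox value meeting SAP 6.1.5.2 after any repeat. Exclude from PP if two or more such visits fall in Day 90 to Day 180, or if three occur in a row at any point in the study.

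This keeps the plan's threshold of two. The run criterion must stay: without it, someone missing Days 30, 60 and 90 but valid at the other three window visits would enter PP, whereas the present list excludes them.

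The cost is one appendix edit before database lock and unblinding, with no new data. PP may gain or lose one or two participants.
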